The incidence rate of SAH is high, 10 per 100.000 among which 85% are caused by a ruptured aneurysm: neurological deterioration is frequent during the ICU stay and is mainly due to delayed cerebral ischemia. The most recent meta-analysis showed that cilostazol significantly reduced poor outcome patients with SAH, with an Odds ratio of 0.52 [0.37 – 0.74] for unfavourable outcome¹⁶. Our trial aims to confirm that a 14 days administration of 100 mg twice a day of cilostazol will reduce by 30% long-term disability and cognitive impairment of aneurysmal SAH. If so, our trial might dramatically change the therapeutic management of aneurysmal SAH, as nimodipine did long time ago. Collective benefit is also expected, including the reduction of the length of hospital stay and need for rehabilitation.

The study protocol will not interfere with other preventive or curative treatment of DCI and vasospasm, which will be kept to the discretion of the physician in charge.

Major secondary effects of cilostazol are arrhythmia, abnormal bleeding, and allergy (frequency not reported). Most frequent adverse reactions are headache (up to 34%), palpitation (up to 10%), and diarrhoea (up to 19%). These side effects are however reported in patients taking cilostazol as a long-term therapy. In previous trial on DCI prevention in SAH, 14 days administration of cilostazol appeared safe since no difference in major adverse events rate was observed between cilostazol and control groups.

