On angiograms in DSA or MR/CTA, the severity of vasospasm will be considered none or mild if there is a less 33% decrease in arterial diameter on angiography, moderate if there is a 34% to 66% decrease, or severe if there is at least a 67% decrease.

DSA or MR/CTA will be performed when:

- There are signs of delayed cerebral ischemia as described above.
- There is a severe impairment of cerebral blood flow velocity assessed with help of transcranial doppler (tCD), as defined below. tCD will be performed at the discretion of the physicians in charge. tCD is a non-invasive radiation free exam that can be used at bedside. Its repetition allows a better detection of vasospasm and is routinely performed. Cerebral vasospasm severity will be evaluated according to this scale:

Degree of cerebral blood velocity alteration	Mean flow velocity (cm/s)	Lindegaard ratio
Mild	120-149	3-6
Moderate	150-199	3-6
Severe	>200	>6

11. Occurrence of new cerebral infarcts

New cerebral infarct is considered when detected on the CT scan or MRI performed with 6 weeks, (or on the latest CT scan or MRI performed before death within 6 weeks, or at autopsy), but not present on the earlier CT or MRI scan performed between 24 and 48 h after early aneurysm occlusion and not ascribable to other causes such as surgical clipping or endovascular treatment. Hypodensities on CT imaging resulting from ventricular catheter or intraparenchymal hematoma should not be considered cerebral infarctions secondary to DCI.

12. Occurrence of cilostazol-related major adverse events, including: arrhythmia, abnormal bleeding and allergy.
13. Occurrence of cilostazol-related minor adverse events include: tachycardia, fever, fainting, nausea, vomiting and stomach pain.

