5.2 Follow-up Visits

Follow up visits will be performed daily from day 1 to day 28. One Brain imaging will be realized 24/48 hours after the aneurism treatment and one between day 28 and 45 after randomization. Transcranial doppler, MR CTA or DSA results will be collected when realized.

Day 1 to day 28

Vital status

Compliance to treatment

Experimental Treatment administration will be collected daily

Safety follow up

- Any major Cilostazol-related adverse event will be assessed:
 - Arrhythmia from auricular origin
 - Arrhythmia from ventricular origin
 - Abnormal bleeding
 - Allergy
- Other minor Cilostazol-related adverse events:
 - Tachycardia,
 - Fever
 - Fainting
 - Nausea
 - Vomiting
 - Stomach pain

Cerebral vasospasm

- Blood flow velocity increase on TCD
- Cerebral vasospasm diagnosed upon MR/CTA or DSA and its severity (mild/moderate/severe)

Delayed cerebral ischemia

- New focal deficit
- Glasgow point decrease
- No other cause

Treatment in the last 24 hours

- Continuous sedation
- Mechanical ventilation
- Extraventricular drain
- Therapy Intensity Level (TIP) for Raised ICP treatment (See Appendix 7)
- Hypertension therapy
- Vasopressors (epinephrine/norepinephrine/dobutamine)
- Milrinone administration
- Endovascular treatment (Balloon therapy or vasodilatator administration)
- Other treatment
- At ICU discharge, the modified Rankin scale will be evaluated by a blinded research technician in case of lost to follow up.

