10.3.3 Specific features of the protocol

All serious and non-serious adverse events must be reported in the CRF.

10.3.3.1 Serious adverse events that do not require the investigator to immediately notify the sponsor

These serious adverse events are only recorded in the "adverse event" section of the case report form.

- **Normal and natural evolution of the pathology:**

Normal and natural evolution of aneurismal SAH is quite variable:

- Even without initial neurological deficit, patients are closely monitored after securisation of the aneurism because of the risk of DCI, vasospasm, hydrocephalus, rebleeding, or any other unspecific complication. Patients in worse neurological condition can be initially intubated; the duration of mechanical ventilation dependst on the subsequent neurological improvement and intercurrent ICU complications.
- Securisation of the aneurism can be performed with endovascular coiling or surgical clipping and lead to ischemic stroke

- Death occurs in approximately 30% of all cases.
- DCI can occur from day 4 until the 21th day after SAH. This risk peaks about the 10th day. DCI can require hypertension therapy and infusion of vasopressor, adjunctive pharmacological treatment, notably milrinone, and endovascular treatment of vasospasm can be requested, but in a centre-dependant way
- Other organ failure might occur as patients might require prolonged ventilatory support and developed ICU related complications, such as nosocomial infection.
- Initial hydrocephalus can worsen the neurological status; it can occur from the first to 15th day. It can require an external ventricular drain. The drain can often be weaned during hospitalisation but if not, internal ventricular drainage can be implanted. It is associated with a risk of nosocomial menigitis.
- When the risk of DCI or other neurological complication is considered low enough, the patient is transferred to the ward until the patient is discharged from the hospital to either the patient's home or a rehabilitation centre.
- **Adverse events likely to be associated with the treatments prescribed as part of the patient's care during the monitoring of the research**

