10.3.3.3 Other events that require the investigator to immediately notify the sponsor

- **Adverse events that are "not serious" but which are significant for the safety of participants**
- The following adverse event will be assessed:
 - Well tolerated arrhythmia from auricular origin
 - Well tolerated arrhythmia from ventricular origin
 - Tachycardia,
 - Fever
 - Fainting

- Nausea
- Vomiting
- Stomach pain
- The investigator must notify the sponsor about these "nonserious" adverse events, in accordance with the same procedures and deadlines as serious adverse events (see section 10.3.4). These events can be considered "medically significant".
- **In utero exposure**

The sponsor must be notified immediately about any pregnancy during which the foetus (from the pre-embryonic stage up to birth) could have been exposed at a given time to an experimental medication, even if the pregnancy is not associated with an adverse event.

Notification is required if the exposure involves:

- the mother,
- the father if the experimental medication is genotoxic.

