12.4 Statistical Analysis and Sensitivity Tests

To ensure robust conclusions, we will apply multiple sensitivity analyses, in addition to ITT and PP analyses:

1. Complete Case Analysis (excluding patients with missing data).
2. Multiple Imputation of missing data to assess the impact of lost-to-follow-up cases.
3. Scenario analysis excluding non-neurological deaths.

Safety analysis

For each patient and each type of toxicity described according to the CTCAE (V.5.0), the worst-case category identified during treatment will be used for the descriptive analysis.

Safety Measures

Safety will be assessed using:

- Incidence of treatment-related adverse events (TEAEs)
- Incidence and severity of treatment-emergent adverse events (TEAEs)
- Incidence of serious adverse events (SAEs)
- Incidence of TEAEs and SAEs leading to discontinuation of study medication.
- Changes in blood chemistry, hematology and coagulation parameter results
- Changes in vital signs including temperature, pulse, respiratory rate, systolic and diastolic blood pressure
- Changes in physical examination results
- Changes in electrocardiogram (ECG) results

These data will be described using lists and tables.

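### The minor adverse event endpoint and its daily checklist leave out headache and diarrhoea, which the protocol names among cilostazol's most frequent reactions

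*Protocol*

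**What the plan says.** The synopsis and section 2.7 describe the drug's known harms. Both state: "Most frequent adverse reactions are headache (up to 34%), palpitation (up to 10%), and diarrhoea (up to 19"%). Both then qualify the figures: "These side effects are however reported in patients taking cilostazol as a long-term therapy".

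Section 4.1.2 sets two safety criteria among the secondary endpoints. Item 12 is "Occurrence of cilostazol-related major adverse events, including: arrhythmia, abnormal bleeding and allergy". Item 13 is "Occurrence of cilostazol-related minor adverse events include: tachycardia, fever, fainting, nausea, vomiting and stomach pain".

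Section 5.2 sets what is checked from day 1 to day 28. Under "Other minor Cilostazol-related adverse events" it lists the same six events as item 13. Section 10.3.3.3, on non-serious events that must still be notified at once, opens with "The following adverse event will be assessed". It gives those six again, plus well-tolerated arrhythmia of auricular or ventricular origin.

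There is also general capture. Section 10.3 has physicians collect adverse events daily and report them through the e-CRF. Section 10.3.3 says "All serious and non-serious adverse events must be reported in the CRF". Section 12.4 plans "Incidence and severity of treatment-emergent adverse events (TEAEs"), and describes toxicity by the worst CTCAE v5.0 category per patient and type.

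**The concern.** The trial sets out to show that cilostazol added to nimodipine is safe as well as superior (section 4.2.1). Item 13 is its prespecified measure of minor drug-related harm. If that measure omits two of the three reactions the protocol calls most frequent, it will tend to make the drug look better tolerated than it is.

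Collection is the second issue. Staff are prompted every day for six events, while headache and diarrhoea depend on someone choosing to record them. Headache is the more exposed of the two. Sudden headache is collected as part of the SAH history in section 5.1, so a clinician may well put a later headache down to the bleed and not enter it as an adverse event. A prompt missed on the day cannot be restored at analysis.

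**Working it through.** No power, error-rate or sample-size figure is involved, and the protocol gives no figure to reproduce. The check compares the lists item by item.

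| Reaction named as most frequent (synopsis, 2.7) | Stated upper rate | Item 12 (4.1.2) | Item 13 (4.1.2) | Daily checklist (5.2) | Notification list (10.3.3.3) |
|---|---|---|---|---|---|
| Headache | 34% | no | no | no | no |
| Diarrhoea | 19% | no | no | no | no |
| Palpitation | 10% | not by name; arrhythmia listed | not by name; tachycardia listed | not by name; both listed | not by name; both listed |

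None of the three is named in any of the four lists. Two of the three have no listed counterpart. The six minor items are identical in 4.1.2, 5.2 and 10.3.3.3, so this is a consistent operating list and not a slip in one place.

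**Scale.** The ceiling is the stated upper rate times the patients per arm (315, section 12.5):

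- headache: 0.34 × 315 = 107.1, about 107 patients
- diarrhoea: 0.19 × 315 = 59.9, about 60 patients
- palpitation: 0.10 × 315 = 31.5, about 32 patients

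These are upper limits. The rates come from long-term therapy and treatment here lasts 14 days. The protocol gives no 14-day rates for these reactions. The figures also do not count the patients missing from item 13: someone with headache and nausea still counts through the nausea. The shortfall is the patients who have an unlisted reaction and none of the six listed ones, and the documents give no overlap from which to estimate it.

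**Effect of unprompted recording.** Suppose a reaction truly occurs in a proportion p₁ on cilostazol and p₀ on placebo, and a fraction s of cases is recorded, the same in both arms because of blinding (an assumption). The observed difference is s·p₁ − s·p₀ = s·(p₁ − p₀). With s below 1, a true excess shrinks but keeps its direction. Prompting matters because it raises s.

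**The case against.** The strongest reply is that the events are captured elsewhere. Daily adverse event collection, the rule that every event enters the CRF, and the planned tables of treatment-emergent events mean that headache and diarrhoea will be recorded and reported by arm. This stands, and it limits the point to the named endpoint and the prompted collection. A reader might infer that these reactions go unrecorded, or that an excess could not be seen without a daily prompt. The protocol supports neither inference: general capture is mandatory, and participants, care providers and assessors are blinded (section 4.2.5), so under-recording should be similar in the two arms.

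A reader might also take the 34% and 19% as rates to expect in this trial. The sentence that follows them in section 2.7 rules that out. It is a reason to expect fewer events, though not a reason to leave them out of the endpoint.

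Palpitation overlaps with tachycardia and arrhythmia, and in sedated patients the sign is easier to establish than the symptom. That stands for palpitation.

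Headache is unspecific after SAH and cannot be reported under sedation. This is a plausible reason to omit it, but the protocol does not give it. Fever is also unspecific in intensive care, and nausea and stomach pain are equally hard to elicit under sedation, yet all three are listed. Nor does the argument reach diarrhoea, which can be observed.

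Finally, item 13 uses a verb that could introduce an open list. The same six items in three sections make that reading weak.

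**Conclusion.** The inconsistency is real and of moderate weight. Item 13 and the section 5.2 checklist omit headache and diarrhoea, which the synopsis and section 2.7 name among the most frequent reactions. Palpitation is a lesser, partly covered gap. As written, the endpoint understates minor drug-related events, and general recording will be less sensitive to a true excess than a daily prompt would be, above all for headache.

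The size is bounded above by about 107 headache and 60 diarrhoea cases in the cilostazol arm, if long-term rates applied in full over 14 days. The true number is probably lower and cannot be fixed from the documents. The conclusion assumes that the six listed items are the operative definition of item 13. The primary endpoint, error rate, sample size, stopping boundaries and serious-event reporting are not affected.

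**What to change.** Add headache (new or worse) and diarrhoea to item 13 in section 4.1.2, to the daily checklist in section 5.2 and to the e-CRF, and name palpitation alongside tachycardia in the same places.

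Reconcile the synopsis and section 2.7 with sections 4.1.2, 5.2 and 10.3.3.3. In particular, state whether the added items join the section 10.3.3.3 list. That list triggers notification on the same procedures and deadlines as serious events. Copying the new items there without thought would make every new or worse headache in an SAH population immediately notifiable, while leaving the list silent would create a fresh mismatch with item 13. Adding the items to the endpoint and the checklist does not require adding them to that list. If the sponsor prefers to keep any of the three out of item 13, the protocol should give the reason.

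The cost is two or three extra tick-boxes a day, so at most 3 × 28 = 84 entries per patient, and some noise in headache recording in sedated or post-SAH patients. The change should be made before the e-CRF is in use, since prompted daily data cannot be collected afterwards.

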4.2 Description of research methodology

4.2.1 Experimental plan

CASH is a multicentre, double-blinded, randomised, placebo-controlled, parallel-group superiority trial in adult, using an adaptive group-sequential design, to demonstrate that cilostazol plus nimodipine is safe and superior to placebo plus nimodipine for improving modified Ranking Score (mRS) at six months.

Two interim analyses for futility and efficacy are planned.

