12 STATISTICAL ASPECTS

12.1 Description of statistical methods to be used including the timetable for the planned interim analyses

CASH is a multicentre, double-blinded, randomised, placebo-controlled, parallel-group superiority trial in adult, using an adaptive group-sequential design, to demonstrate that cilostazol plus nimodipine is safe and superior to nimodipine alone will improve modified Ranking Score (mRS) at six months.

Two interim analyses for futility and efficacy are planned.

Populations

For the statistical analysis, the following populations are defined:

Population	Description
Intent-To-Treat (ITT) Population	The ITT population will include all randomised participants. ITT participants will be analysed according to the randomised treatment, regardless of the actual treatment received. All efficacy analyses will be performed on the ITT population.
Per Protocol (PP) Population	The PP population will include all participants in the ITT with at least 80% of doses received to define adherence to treatment. The PP population will be used for supportive analyses of efficacy measures.
Safety Population (SP)	The SP will include all randomised participants who received at least one treatment (active or placebo). The SP will be analysed according to the actual treatment received. This population will be used for safety analyses.

Description of the statistical methods, including the timing of planned interim analyses

The statistical analysis plan (SAP) will be developed and finalised before the database is locked.

Below is a description of the planned statistical analysis. Further details will be presented in the statistical analysis plan (SAP).

All statistical analyses will be performed with SPSS version 26 or RStudio. For analyses performed with RStudio, the script used will be provided.

The baseline is defined as the last evaluation performed before the start of the study treatment, day 1 (V1).

All data collected after the start of the study treatment are defined as post-baseline.

Baseline characteristics will be summarised by the treatment group. The mean and standard deviation (SD) or median and interquartile range (IQR) for skewed variables will be summarised for continuous measures.

The proportion in each category will describe categorical variables.

In addition, the 95% confidence interval (CI) will also be calculated as indicated.

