The time-to-event variables will be analysed using the Cox proportional hazards model, including randomisation arm, age (as a continuous variable), severity at inclusion, and centre as model terms. The hazard ratio between the arms will be presented with the 95% CI and p-value of the model. Kaplan-Meier curves will be presented by the arm for each appropriate endpoint.

For the primary objective, both overall and by subgroups, the following statistics will be provided: effect size, confidence intervals, number needed to treat and absolute risk reduction as appropriate.

All tests will be two-sided with a unilateral significance level of 0.025% adjusted for the interim analysis.

Subgroup analyses

Subgroup analyses will be performed to assess the consistency of the treatment effect between subgroups without multiplicity adjustment. The following subgroups will be assessed for the primary endpoint:

- Fisher grade I to III versus IV
- Age: <50 years; >=50 and <=70 years; >70 years

The treatment effect for the total population and subgroups will be represented using forest plot graphs.

For HR and OR in subgroup analyses, the significance of the interaction will be tested using the method proposed by Altman & Bland 2003.

Treatment of missing data

For the analysis of the primary endpoint, in the event of study exit prior to evaluation of the primary endpoint (6 months), the last recorded mRS value will be used (LOCF method, mRS at ICU discharge) patients will be considered as non responders if no mRS are recorded.

For all other variables, in case of a significant proportion of missing data (>10% of subjects), a sensitivity analysis using multiple conditional imputation techniques by chained equations (MICE) will be performed, according to a conservative principle, using the mean severity at inclusion as the central position parameter and an estimate of the intra-patient variability in the placebo group as the dispersion parameter. Sensitivity analysis based on imputed data will be considered secondary.

Further details on the treatment of missing data will be provided in the SAP.

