In light of the results obtained for the sample size estimation, an OR between the two arms of 1.86 is assumed as a precaution. This assumption sets the proportion of patients who will obtain a favourable outcome in the control arm at 65% and the proportion of responders in the experimental arm at least 76%. These proportions may appear high, but it should be noted that the study does not include patients with early death and without surgery.

The experimental design includes two intermediate analyses; a sequential group test and the O'Brian-Fleming Analog spending function for alpha and beta errors were used.

Therefore set unilateral alpha at 0.025 and the power of the test (1-beta) at 0.80, 284 patients are needed per experimental arm; details are given in table 3 and figure 1.

A drop-out rate of no more than 10% is expected so that the sample size will be 630 patients (315 per experimental arm).

All estimates for the interim analyses are made without considering the inflation quota for drop-out patients. Therefore this evaluation will be made at the planned number of patients who completed the study. Only the final analysis will bear any inflationary share of the sample.

Table 3. Summary Report -

Item	Value
Maximum Number of Stages (Design):	3
Current Stage:	0
Alternative Hypothesis:	$P1 - P2 < 0$ (one-sided)
Alpha Spending Function:	O'Brien-Fleming Analog
Beta Spending Function:	O'Brien-Fleming Analog
Futility Boundaries:	Binding
Target Alpha:	0.025
Alpha (from simulations):	0.025
P1:	0.65
P2:	0.76
N1 (if final stage reached):	284
N2 (if final stage reached):	284
Target Power:	0.8
Power (from simulations):	0.8016
Maximum Information:	692.8

Information Report

Maximum Information: 692.8519

 Alternative Hypothesis: $P1 - P2 < 0$ (one-sided)

Alpha: 0.0250

Stage	Target information proportion	Target sample size N1	Target sample size N2	P1	P2
1	0.33	95	95	0.65	0.76
2	0.67	189	189	0.65	0.76
3	1.00	284	284	0.65	0.76

Alpha Spending

Target Final Stage Alpha: 0.0250

Spending Function: O'Brien-Fleming Analog

Stage	Information proportion	Alpha spent this stage	Cumulative alpha spent	Percentage alpha spent at this stage	Cumulative percentage
1	0.33	0.0001	0.0001	0.4	0.4
2	0.67	0.0059	0.0060	23.8	24.2
3	1.00	0.0190	0.0250	75.8	100.0

Beta Spending for Futility

Target Cumulative Beta at Final Stage: 0.2000

Spending Function for Futility: O'Brien-Fleming Analog

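### The protocol aims to demonstrate that cilostazol is safe, but plans only a descriptive safety analysis in a trial sized on the mRS alone.

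*Protocol*

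**What the plan says.** Section 4.2.1 describes a superiority trial whose purpose is "to demonstrate that cilostazol plus nimodipine is safe and superior to placebo plus nimodipine". Section 12.1 repeats this with a different comparator phrase: "to demonstrate that cilostazol plus nimodipine is safe and superior to nimodipine alone".

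The efficacy half is worked out in section 12.5: "Therefore set unilateral alpha at 0.025 and the power of the test (1-beta) at 0.80, 284 patients are needed per experimental arm". The assumed mRS response rates are 65% on control and 76% on cilostazol, and 315 per arm are to be randomised to allow for drop-out.

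For safety, section 12.4 takes each patient's worst CTCAE category for a descriptive summary, lists the safety measures, and closes: "These data will be described using lists and tables". Section 4.1.2 numbers arrhythmia, abnormal bleeding and allergy among the secondary criteria (item 12). The comparative methods in section 12.1 deal with the mRS and time-to-event variables and name no analysis for these harms. The list of objectives in section 3.2 is more modest and ends by saying only that cilostazol-related events will be monitored.

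Oversight is described elsewhere. Section 5.8.4 allows termination if serious adverse reactions differ between arms, section 10.3.7 gives the DSMB a role in validating termination criteria, and section 12.7 has the IDMC review interim safety data. None of these states a number.

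**The concern.** A trial that says it will demonstrate safety needs something that could demonstrate it: a limit on acceptable excess harm, or at least an estimate of the excess with its uncertainty. Tables by arm provide neither. They show counts, and the reader has to judge what excess the data rule out.

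This matters here because section 2.5 calls cilostazol an antiplatelet agent, it is given after an intracranial haemorrhage, and section 2.7 names abnormal bleeding and arrhythmia among its major effects. These harms are what any gain on the mRS must be weighed against. If they are uncommon, an unremarkable table is quite likely even when the true rate has doubled, and with the aim worded as it is, such a table could end up under a claim of demonstrated safety.

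**Working it through.** **The plan's own figure.** Inputs from section 12.5: 0.65 against 0.76, one-sided alpha 0.025, power 0.80.
- Fixed design: n = [1.96 × √(2 × 0.705 × 0.295) + 0.8416 × √(0.65 × 0.35 + 0.76 × 0.24)]² / 0.11² = 269 per arm.
- Maximum information at 284 per arm: 284 / (0.2275 + 0.1824) = 692.85, as printed.
- Simulating the three looks (95, 189 and 284 per arm) with the printed boundaries gives power 0.801 to 0.802; the plan states 0.8016.

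The size reproduces, and every input to it is an mRS response rate. No safety quantity enters.

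**What 315 per arm can detect on harms.** The safety population is all randomised and treated patients, so 315 per arm is the right count at full enrolment. Section 2.7 says the frequency of the major effects is not reported, so the control rate c is assumed over a range. The benchmark is a two-sided 5% two-proportion test for a doubling from c to 2c:

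miss = 1 − Φ[(c − 1.96 × SE0) / SE1], with SE0 = √(2p̄(1 − p̄)/n), p̄ = 1.5c, and SE1 = √([c(1 − c) + 2c(1 − 2c)]/n).

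| Doubling | SE0 | SE1 | Miss, 315 per arm |
|---|---|---|---|
| 2% to 4% | 0.01359 | 0.01357 | 68.8% |
| 3% to 6% | 0.01652 | 0.01648 | 55.7% |
| 5% to 10% | 0.02099 | 0.02089 | 33.6% |
| 10% to 20% | 0.02845 | 0.02817 | 5.8% |

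Exact enumeration of the chi-square test gives 68.6% and 32.2% for the 2% and 5% rows; Fisher's exact test gives 75.9% and 38.1%.

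**After an efficacy stop.** The boundary table in section 12.5 gives 0.0253 + 0.4166 = 0.44 as the probability of stopping for efficacy by the second look under the planning assumptions. That look takes place at 378 six-month completers, but patients enrolled since then also contribute harm data. With uniform accrual of 630/42 = 15 a month, the six-month lag adds 90: (378 + 90)/2 = 234 treated per arm. The same formula gives 75.6% (2% to 4%), 65.4% (3% to 6%) and 46.3% (5% to 10%). If 10% drop-out means that 378/0.9 = 420 were randomised to yield the completers, then (420 + 90)/2 = 255 per arm, and the 2% and 5% rows become 73.8% and 42.7%.

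**What an interval would show.** With equal observed rates p and 315 per arm, the 95% half-width for the risk difference is 1.96 × √(2p(1 − p)/315): 2.2 points at 2%, 2.7 at 3%, 3.4 at 5%. At 2% a doubling (2 points) is not excluded; at 5% a doubling (5 points) is. The interval makes this distinction visible, and a table of counts does not.

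**The case against.** The best defence is that this is one loose word in a design sentence. The primary objective in section 3.1 is the mRS alone, section 3.2 promises only to monitor adverse events, and section 12.1 defers further detail to the SAP. Risk differences with intervals for adverse events are common SAP content, so their absence from a protocol is not by itself a fault. Arms will in any case be tabulated side by side, death counts within the primary scale, and 28-day mortality is a secondary criterion.

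Much of this stands. It does not remove the mismatch, because the protocol states both the aim and the method. An SAP could add intervals, but the claim to demonstrate safety would remain in two sections of the protocol.

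Four stronger readings are tempting and not supported:
- **That the trial will declare safety if no difference is seen.** A reader might infer this from section 2.7, where cilostazol "appeared safe since no difference in major adverse events rate was observed between cilostazol and control groups". That sentence is background on earlier trials; no section says how this trial will conclude safety.
- **That there is no safety control beyond tables.** Committee review and the trigger for unequal serious reactions are part of the plan, and numerical rules may stand in a charter not shown.
- **That harm data after a stop at the second look rest on 189 per arm.** Those are six-month completers, not the safety population.
- **That the earlier trials were too small to exclude a relevant excess.** They were small (one had arms of 23 and 27), but the protocol gives no adverse-event counts from them, so it cannot support that statement either.

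**Conclusion.** The point holds as a mismatch between a stated aim and a stated method: sections 4.2.1 and 12.1 promise a demonstration of safety, section 12.4 provides description only, and section 12.5 sizes the trial on the mRS. The committee provisions govern whether the trial continues, not what the final report may claim.

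The size depends on two assumptions. The background rates are not in the protocol, and the benchmark is a 5% test that the protocol does not plan for harms. On those terms a doubling of a 2% to 5% harm would be missed about 69% to 34% of the time at 315 per arm, and about 76% to 46% at roughly 234 per arm after an efficacy stop at the second look, given uniform accrual. For a 10% harm at full enrolment the miss rate is about 6%, so the limitation concerns uncommon harms. These figures are not the error rate of any planned safety decision. The mRS sample size and the efficacy analysis are unaffected.

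**What to change.** 1. In sections 4.2.1 and 12.1, limit the claim to superiority and add that safety will be estimated.
2. In section 12.4, for death, any serious adverse event, abnormal bleeding and arrhythmia, report the between-arm risk difference in the safety population with a two-sided 95% confidence interval. Do the same after an early stop, using all treated patients and not only six-month completers.
3. In the same section, state that the absence of a visible or statistically significant difference will not be reported as evidence of safety.

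The background statement on earlier trials in section 2.7 can stay as it is.

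Cost: a few lines of wording and one table from data already collected; no extra patients, visits or change to treatment. The downside is that the trial gives up an unqualified claim of demonstrated safety.
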